***The effects of Patiromer on serum potassium level
and gut microbiome of ESRD patients with
hyperkalemia***

Protocol #: R-01

Principal Investigator: [name]

Version #: 1.4

Version Date: July 25, 2017

STATEMENT OF COMPLIANCE

STUDY TITLE	The effects of Patiromer on serum potassium level and gut microbiome of ESRD patients with hyperkalemia
PROTOCOL NUMBER	R-01
PROTOCOL VERSION	v1.4
VERSION DATE	July 01, 2017
STUDY SPONSOR	Relypsa

DECLARATION OF THE INVESTIGATOR:

The study will be conducted in accordance with the International Conference on Harmonization (ICH) document “Guidance for Industry – E6 Good Clinical Practice: Consolidated Guidance” dated April 1996 and the Code of Federal Regulations on the Protection of Human Subjects (45 CFR Part 46). The Principal Investigator will assure that no deviation from, or changes to the protocol will take place without prior agreement from the sponsor and documented approval from the Institutional Review Board (IRB), except where necessary to eliminate an immediate hazard(s) to the study subjects. All personnel involved in the conduct of this study have completed Human Subjects Protection Training.

Further, I will conduct the study in keeping with local legal and regulatory requirements.

NAME (Print): _____

SIGNATURE: _____

DATE: _____

PROTOCOL SYNOPSIS

Study Title:	The effects of Patiromer on serum potassium level and gut microbiome of ESRD patients with hyperkalemia
Phase:	Phase 2, safety and efficacy trial
Primary Objective:	To examine the tolerability, safety, and efficacy of Patiromer in lowering serum potassium levels in ESRD patients that are on maintenance dialysis with hyperkalemia (K>5.0 mEq/L).
Secondary Objective:	To assess the changes in gut microbiome and serum metabolom profiles of hyperkalemic ESRD patients treated with Patiromer.
 Study Design:	 This is a non-randomized, crossover study. 25 ESRD patients with hyperkalemia (K>5.0 mEq/L) will be enrolled in an open-label, pilot clinical trial with 3 sequential phases of (a) 2 weeks of no intervention, (b) 12 weeks of Patiromer treatment, and (c) 6 weeks of no intervention. Treatment with Patiromer will be initiated at a dose of 8.4 gram, once daily and observed for a week, then uptitrated to 16.8 g once daily. Eligible subjects will collect stool samples and provide blood and urine samples.
Study Duration:	The total anticipated study duration is approximately 2 years, with anticipated enrollment duration of 9 months, and anticipated study conduct duration upon full enrollment of 3 months. The remaining 12 month will needed for data analysis.
Study Population	The study will enroll approximately 25 adult male or female subjects between the ages of 18-85 years. Subjects with diabetes or HIV will also be enrolled.
Study Products:	Patiromer is an FDA-approved orally administered drug used for the treatment of hyperkalemia. It is a non-absorbed polymer that binds potassium throughout the gastrointestinal tract and leads to

lowering serum potassium levels (1). Prior Patiromer clinical trials have demonstrated the drug's utility in treating hyperkalemia in patients with diabetic kidney disease (1; 2).

Key Roles

Principal Investigator (responsible for study conduct and all site-related medical decisions)	[name] [name] [contact] Email: [contact]
Clinical Laboratory and Laboratory Director	[name] Address: [name]

1 Introduction: Background and Scientific Rationale

1.1 Background

1.1.1 Gut Microbiota

Human gut harbors a complex community of over 100 trillion microbial cells, which constitute the microbiota (3). The gut microbiome encodes about 3.3 million genes, which is 150 times that of our own genome (4). The symbiotic gut microbiota provides complementary biological and metabolic functions that cannot be performed by humans (5). Disruption to the normal balance between the gut microbiota and the host (dysbiosis) is associated with diverse disease states such as obesity, inflammatory bowel disease, neurological disorders, cancer, and cardiovascular disease (CVD) (6-11).

Findings from the human microbiome project (HMP) revealed that the gut microbiome is highly specific, personalized and functionally relevant to health (12). Gut microbiota is altered in patients with chronic kidney disease (CKD). Preliminary evidence indicates that the dysbiotic gut microbiota could be the source for a plethora of uremic toxins (13), many of which have been shown to be positively correlated with progression of CKD and increased risk for major adverse cardiovascular events defined as death, myocardial infarction, or stroke (14-16). Therefore, correcting the gut microbiota dysbiosis might be a therapeutic option for reducing both the progression as well as the cardiovascular burden of CKD.

Hyperkalemia, a frequent and serious electrolyte abnormality in patients with kidney failure, can lead to life threatening cardiac arrhythmias (17; 18). Even relatively mild (5.5 to 6.0 mEq/L) hyperkalemia is associated with an increased risk of mortality (19). Compensatory increase in fecal potassium excretion occurs in patients with renal failure (20; 21). Normally, the gut is responsible for only 5% of total potassium excretion; however, in patients with end-stage renal disease (ESRD), this can increase substantially to account for 30% to 50% of potassium excretion (22).

Preliminary evidence indicates that the growth rate of certain bacteria is affected by the increasing concentration of potassium in the growth medium (23). *E. coli* populations exhibited higher growth rates in the presence of additional potassium (23). However, potassium may also

adversely affect the growth of commensal methanogens. At increased concentrations, potassium decreases methanogenesis by entering cells through membrane leaks or via a potassium transport carrier, thus decreasing the transmembrane electron potential (24). This has been shown to have a significant impact on the pH regulation of the bacteria (25).

Patiromer for oral suspension is an FDA-approved orally administered drug used for the treatment of hyperkalemia. It is a nonabsorbed polymer that binds potassium throughout the gastrointestinal tract and leads to lowering serum potassium levels (1). Prior Patiromer clinical trials have demonstrated the drug's utility in treating hyperkalemia in patients with diabetic kidney disease (1; 2).

1.1.2 Rationale for Study and Study Design

This study will add to the body of data and expand the knowledge about the tolerability, safety, and efficacy of Patiromer in lowering serum potassium levels in ESRD patients with hyperkalemia. Furthermore, the study will examine changes in gut microbiome and serum metabolome profiles of hyperkalemic ESRD patients treated with Patiromer in order to determine the impact of lowering gut potassium levels using Patiromer on gut microbiome dysbiosis and generation of uremic toxins. We anticipate that Patiromer will improve the metabolomics profile and gut permeability through binding to and removing endotoxin and bacteria-generated uremic toxins, and by altering the microbiome profile in ESRD patients. In addition, this study will unravel the effect of hyper/normo-kalemia on plasma metabolom.

1.2 Potential Risks and Benefits

1.2.1 Known Potential Risks

Patiromer is fairly safe and approved by the FDA. Most commonly observed side effects are hypomagnesaemia and constipation. The other study related risks is associated with the study procedures, which is the blood draws.

1.2.2 Known Potential Benefits

There are no benefits for study participants.

The study will add to the knowledge on the gut dysbiosis in subjects with ESRD on hemodialysis, the safety and efficacy of Patiromer, and changes in gut microbiome and serum metabolic profiles of hyperkalemic ESRD patients treated with Patiromer.

1.3 Study Objectives

1.3.1 Primary Objective

- Examine the tolerability, safety, and efficacy of Patiromer in lowering serum potassium levels in ESRD patients with hyperkalemia ($K>5.0$ mEq/L). In a non-randomized, crossover study, 25 ESRD patients with hyperkalemia ($K>5.0$ mEq/L) will be enrolled in an open-label, pilot clinical trial with 3 sequential phases of (a) 2 weeks of no intervention, (b) 12 weeks of Patiromer treatment at 8.4-16.8 g/day, and (c) 6 weeks of no intervention. Blood and stool samples will be collected throughout the study period.

1.3.2 Secondary Objectives

- Determine the changes in gut microbiome and serum metabolome profiles of hyperkalemic ESRD patients treated with Patiromer. Blood and stool samples collected from the ESRD patients enrolled in the above study will be collected at pre-specified time points and analyzed by metagenomics for gut microbiome profiles, and untargeted and targeted metabolomics for stool and serum metabolome profiles, in order to determine the impact of lowering gut potassium levels using Patiromer on gut microbiome dysbiosis and generation of uremic toxins.

2 STUDY DESIGN AND ENDPOINTS

2.1 Overview of Study Design

This is an intervention study in subjects with ESRD on hemodialysis. After a screening visit, all eligible subjects will collect stool and provide blood samples according to Table 1.

2.2 Study Endpoints

2.2.1 Primary Endpoint

- For Specific Aim 1, the primary safety end point is adverse events during the 12 weeks of intervention.
- For Specific Aim 2, the primary efficacy end points will be change in microbiome, metabolome and markers of inflammation.

2.2.2 Secondary Endpoints

- For Specific Aim 1, the Secondary efficacy end points included mean change in serum potassium level through 12 weeks.

2.3 Blinding

This sampling study will not be blinded.

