3 STUDY ENROLLMENT AND WITHDRAWAL

This is a non-randomized, crossover study. 25 ESRD patients with hyperkalemia ($K>5.0$ mEq/L) will be enrolled in an open-label, pilot clinical trial with 3 sequential phases of (a) 2 weeks of no intervention, (b) 12 weeks of Patiromer treatment, and (c) 6 weeks of no intervention.

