6 STUDY PROCEDURES AND SCHEDULE

6.1 Study Procedures/Evaluations

6.1.1 Study Specific Assessments and Procedures

This section describes the study specific assessments and procedures that will be conducted. Results from study specific procedures (e.g., laboratory evaluations or questionnaire results) will not be provided to subjects, unless the results are necessary in order to effectively communicate follow-up care for any adverse events that may occur as a result of participating in the study.

[figure not shown]

Figure 1. Sample collection. Stool and blood samples will be collected at weeks 1, 2, 3, 4, 6, 10, 14, 17 and 20 of the study. We will obtain information regarding dietary pattern and gastrointestinal health. Adverse events related to study drugs, and clinical events will also be collected. Patients will be requested to complete gastrointestinal (GI) health assessment survey at baseline, during treatment, and during post-treatment phase. Detailed information about infection and type of antibiotic used (if any) will be collected.

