6.2.1.4 Metabolic and inflammatory biomarker studies

Blood and stool samples will be stored for metabolomics and biomarker studies. Both non-biased and targeted metabolomics profiling of the stool and blood will be performed at the West Coast Metabolomics Center at the University of California Davis. Filtered fecal water or plasma samples will be used for the mass spectrometry-based metabolomics profiling. The process of metabolite extraction will include internal standards and follow standard protocol. The resulting extract will be divided into a liquid chromatography fraction and a gas chromatography fraction.

6.2.1.5. Measurement of biomarkers of inflammation: Measurement of endotoxin, sCD14, hs-CRP, IL-6 and TNF- α will be performed at weeks 1, 2, 6, 10, 14, 17 and 20 of the study. Plasma LPS levels will be measured using a commercially-available kinetic chromogenic limulus amebocyte lysate assay kit (Lonza Walkersville, Walkersville, MD). High sensitivity sandwich ELISAs will be used to measure plasma sCD14, hs-CRP, IL-6, and TNF α . The samples will be stored at -80°C and assayed at the time of initial thawing to prevent degradation. All cytokine assays will be performed in duplicates. If funds are available, we will also measure IL-1 β , IL-2, IL-4, IL-17, IL-10, and IL-22.

6.2.1.6 Measurement of specific uremic toxins and bacterial metabolites in plasma:

Measurement of plasma p-cresol sulfate, indoxyl sulfate, TMAO and SCFA will be performed at 2, 4, 10, 14 and 20 weeks of the study. Plasma will be separated from whole blood samples collected in tubes containing EDTA as anti-coagulant. Extracted plasma will be frozen immediately after collection and store at -80°C until further use. The chromatographic separation of metabolites will be performed using either reverse phase separation or normal phase online with QQQ mass spectrometers (Agilent Technologies). For this, we will employ a combination of solvents including gradients at varying concentrations of ammonium acetate, methanol, acentonitrile adjusted for specific metabolites. Metabolites will be separated by controlled flow rates on either a Luna Phenyl Hexyl column (3um, 2x150mm, Phenominex), a Luna Amino (NH2) column (4um, 100A 2.1x150mm, Phenominex), or an orbax Eclipse XDB-C18 column (50 x 4.6 mm i.d.; 1.8 µm, Agilent Technologies, CA), while adjusting the temperature of the chamber. All the columns used in this study will be washed and reconditioned after every 50 injections.

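### Nothing masks the staff who select, assay and process the Aim 2 research samples to study week, although these primary efficacy readouts come from stored samples and could be handled blind

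*Combined protocol and SAP*

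**What the plan says.** - **Blinding.** Section 2.3 reads, in full, "This sampling study will not be blinded". It makes no exception for laboratory, bioinformatics or analysis staff, and it does not mention them.
- **Endpoints.** Section 2.2.1: "For Specific Aim 2, the primary efficacy end points will be change in microbiome, metabolome and markers of inflammation". All three are assay or sequencing outputs.
- **Design.** Section 3 describes "3 sequential phases of (a) 2 weeks of no intervention, (b) 12 weeks of Patiromer treatment, and (c) 6 weeks of no intervention". There is one sequence and no concurrent control.
- **Expected direction.** Section 1.1.2: "We anticipate that Patiromer will improve the metabolomics profile and gut permeability".
- **Sampling.** Section 6.1.1 (Figure 1 legend): "Stool and blood samples will be collected at weeks 1, 2, 3, 4, 6, 10, 14, 17 and 20 of the study". Section 6.2.1.5 measures the inflammation markers at weeks 1, 2, 6, 10, 14, 17 and 20.
- **Sample identity.** Section 6.3.3 gives each participant one five-digit number. Section 8.4 says that stored samples are de-identified. Both conceal the person; neither conceals the visit.
- **Handling rules.** A footnote to Table 1 (section 6.3.1) says that stored blood and stool will be analysed purposefully, and gives no selection rule. Section 6.2.1.5 says "All cytokine assays will be performed in duplicates", with no limit for discordance and no re-assay rule. Section 6.2.2.1 names the instrument for DNA quality control but no pass/fail criterion. The same section does fix the read-trimming threshold, the removal of duplicate reads, the alignment options and the filtering of human reads.

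**The concern.** Patients and treating staff cannot reasonably be blinded in this design. The laboratory work can be, because the research samples are stored and analysed later. With a fixed off-on-off order, anyone who knows the week on a tube knows whether the patient was on Patiromer.

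With no control arm, the Aim 2 result is a comparison of on-drug with off-drug tubes. Protection against observer bias therefore rests on treating the two kinds of tube alike. If someone who knows the phase, and expects improvement, decides which samples are worth analysing, which DNA extract failed or which discordant duplicate to set aside, modest one-sided choices can look like a drug effect on the primary efficacy endpoints.

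**Working it through.** **1. Is there any masking in the documents?** Reading sections 2.3, 6.2, 6.3.3 and 8.4 together, none is described. No laboratory manual that might contain it is referenced. Metabolomics is done at an outside university core laboratory, and nothing says what appears on the tubes sent there.

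**2. How many research samples are involved?** With 25 patients:
- stool: 25 × 9 = 225
- inflammation markers: 25 × 7 = 175
- metabolomics (Table 1): 25 × 5 = 125

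**3. How much could phase-aware handling matter?** The plan gives no alpha, test or SD for these markers, so there is no stated figure to reproduce. The following is a simulation with no drug effect.

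Inputs from the documents: 25 patients; pre-drug weeks 1 and 2 (25 × 2 = 50 values); on-drug weeks 6, 10 and 14 (25 × 3 = 75 values).

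Assumptions:
- one normally distributed marker on the log scale, within-patient SD 1, lower is better
- d = mean(weeks 6, 10, 14) − mean(weeks 1, 2) for each patient, with a paired t-test at two-sided 0.05, so 2.5% in each direction
- 4 or 8 on-drug values set aside: 4/75 = 5.3%, 8/75 = 10.7%
- between-patient SD of 0, 1 or 1.5. ICC = between-patient variance / (between + within): 0; 1/(1 + 1) = 0.5; 2.25/(2.25 + 1) = 0.69

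False findings in favour of the drug (ranges are across repeat runs of 4,000 to 6,000):

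| Values set aside | 4 of 75 | 8 of 75 |
|---|---|---|
| Highest on-drug values, ICC 0 | 9.2–9.9% | 20.0–20.8% |
| Highest on-drug values, ICC 0.5 | 6.9–7.1% | 14.2–15.1% |
| Highest on-drug values, ICC 0.69 | 6.4% | 11.7% |
| Random from top quarter of on-drug values, ICC 0.5 | 4.6% | 8.2% |
| Random from top half of on-drug values, ICC 0.5 | 3.5% | 5.2% |

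For reference, with nothing set aside the rate is 2.2–2.9%. When the same share of all values is removed without regard to phase, it is 2.5–3.0% at ICC 0 and 0.5. At a rate of 10% and 4,000 runs, the simulation standard error is √(0.10 × 0.90 / 4000) = 0.5 percentage points, so differences of that order are noise.

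**4. A second rule.** Suppose low pre-drug values and high on-drug values (beyond 1 SD) are both liable to be discarded, with ICC 0.5 and 20,000 runs. Phase-aware discarding of 1.6%, 4% and 8% of all values gives two-sided error of 5.2%, 7.5% and 17.2%. Discarding the same shares blind to visit gives 4.7–5.3%. Light selection barely matters; heavier selection does.

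**5. What coding alone would not cure.** If assay batch lines up with phase, a shift of 0.1, 0.2 or 0.3 SD (total SD 1, ICC 0.5) gives two-sided error of 11%, 33% and 60%, even with perfect tube codes. Batching therefore has to be part of the remedy.

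**The case against.** The best case for the plan is that section 2.3 describes how treatment is given and says nothing about laboratories. A reader might infer that the plan commits laboratory staff to knowing the week. The documents do not support that: the lack of masking follows from blanket wording plus silence elsewhere, and the laboratories may code samples in practice.

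Some steps that look like judgement are also less open than they seem:
- Read processing is fixed in section 6.2.2.1, so it should not be counted as discretionary.
- The open choice of separation mode and column in section 6.2.1.6 reads as a choice per metabolite, applied to all tubes.
- Section 6.2.1.5 has samples assayed at first thaw, which limits later selective repeats.
- Peak integration and outlier calls are not described in the plan. That they involve judgement is a reviewer's inference.

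On size, a reader might take 10 to 20% as the expected error. That figure needs no between-patient variation and removal of exactly the most extreme on-drug values. It also concerns one scalar marker. Nothing has been calculated for the microbiome or metabolome profiles, or for the comparison with off-drug weeks 17 and 20.

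All of this stands, and it limits the size. It does not remove the gap: sample selection, DNA quality control and duplicate assays have no stated rule, and the people applying them are not masked.

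**Conclusion.** The point holds as a design weakness that is cheap to close. It is not evidence that bias has occurred or will occur. The plan describes no masking to study week for staff handling the Aim 2 research samples, and leaves at least three steps to their discretion.

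Under the assumptions above (no drug effect, one scalar marker, paired t-test, 5 to 11% of on-drug values set aside with knowledge of phase, ICC 0 to about 0.7), false findings in favour of the drug rise from about 2.5% to about 4 to 20%. The share set aside, the ICC and the selection pattern are all assumed. The firm result is the contrast: the same share removed blind to phase leaves the rate at about 2 to 3%.

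It would be wrong to infer that masking makes the on/off comparison unbiased. Period effects, regression to the mean after selecting patients for high potassium, and storage-time differences all remain in an uncontrolled sequence.

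**What to change.** Reword section 2.3 to say that treatment is open-label, but that staff who select, assay, process and quality-control the research aliquots (metagenomics, metabolomics, uremic toxins, inflammation markers, zonulin) are blinded to study week. Then specify:

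1. Research aliquots carry random codes that show neither week nor visit order.
2. All of a patient's visits are run in the same assay batch, in random order.
3. The study coordinator holds the key until decisions on sample selection, repeats, exclusions and peak integration are locked.
4. Safety tests (potassium, magnesium, metabolic panel, blood count) are exempt and stay identifiable.

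The cost is relabelling and key-keeping by existing staff, plus waiting to batch: a week 1 sample would wait up to 20 − 1 = 19 weeks for that patient's last visit. Section 6.2.1.5 already provides for storage at −80°C. No extra patients, visits, samples or assays are needed. The change should be in place before research samples are labelled and analysed, because knowledge of phase cannot be withdrawn afterwards.

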3 STUDY ENROLLMENT AND WITHDRAWAL

This is a non-randomized, crossover study. 25 ESRD patients with hyperkalemia ($K>5.0$ mEq/L) will be enrolled in an open-label, pilot clinical trial with 3 sequential phases of (a) 2 weeks of no intervention, (b) 12 weeks of Patiromer treatment, and (c) 6 weeks of no intervention.

3.1 Inclusion Criteria

Subjects must meet all of the following criteria in order to be enrolled into the study:

1. Subjects on stable hemodialysis for more than 90 days
2. Age 18-85 years
3. Persistent hyperkalemia, defined as elevated serum potassium >5.0 mEq/L in more than 2 occasions during the previous 3 months.
4. Ability to provide informed consent

3.2 Exclusion Criteria

Subjects must not meet any of the following criteria in order to be enrolled into the study:

1. Use of pre- or probiotics during the past 2 months
2. Use of antibiotics within the past 2 months, if the patient received a single course of antibiotic.
3. Presence of chronic wound infection and osteomyelitis
4. Inflammatory bowel disease, chronic diarrhea, current *C. difficile* infection
5. Liver cirrhosis or chronic active hepatitis
6. Treatment with immunosuppressive medications in the past 6 months or more than a week of treatment with prednisone >10 mg in the last 3 months
7. Anticipated kidney transplant within 9 months
8. Expected survival < 9 months
9. Pregnancy, anticipated pregnancy, or breastfeeding
10. Incarceration
11. Participation in another intervention study
12. Severe anemia defined as hemoglobin <8.0 g/dl any time during the last 2 months

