3.3 Strategies for Recruitment

Subjects will be recruited through a search of the dialysis unit database. Potentially eligible subjects resulting from this database search may then be approached and offered a Screening Visit if interested to participate. It is anticipated that approximately 120 potential subjects will be screened in order to enroll 25 eligible subjects, reflecting an expected screen failure rate of ~80%. 36 weeks is the anticipated timeframe for recruitment.

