6.3.2 Screening Visit (Week 0)

Patients who appear eligible based on pre-screening will be approached in person to determine interest in participation and confirm eligibility. Study personnel will discuss the study goals and procedures with the potential participant in detail. Patients should have an understanding of the importance of providing frequent stool samples and what the process entails. If the patient agrees to participate in the study, study personnel will review and assess understanding of the entire informed consent form prior to obtaining written informed consent from the participant. The consenting process will be performed by a qualified investigator or study site designee. Informed consent will be obtained and documented before any study procedures are performed.

The following activities may take place over one or two visits.

- Determination of eligibility
- Informed consent process
- Collection of baseline data including demographics, medical history, and medication use including recent and current use of prescription products, over-the-counter products, herbal supplements, vitamins, and prebiotic and probiotic use in any form. In addition, medical records from the clinic facility will be reviewed to capture any non-reported data on recent medication use.

- Blood draw (13mL): Blood samples collected at Screening will be tested for the CMP, CBC, phosphorous and PTH.
- Serum pregnancy test for women of childbearing potential and tested at local lab.
- Instruction in stool sample collection and storage
- Instruct enrolled participants **not to change their dietary patterns**, if possible, during the study

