6.3.4 Stool Sample Collection

Subjects will be provided with detailed instructions on how to collect and store their stool samples. Subjects will be instructed to collect samples from bowel movements at weeks 1, 2, 3, 4, 6, 10, 14, 17, and 20.

7 Evaluations and Follow Up

Participants will have in-person study visits at Weeks 1, 2, 3, 4, 6, 10, 14, 17 and 20. At each study visit, participants will be asked about emergency room visits, hospital admissions or any significant clinical events that occurred since the last visit. RCs will have weekly contact with participants to query them on antibiotic use in the previous week and medical records will be reviewed for blood potassium levels and antibiotics administered.

Dietary assessment using the Block Food Frequency Questionnaire (<https://nutritionquest.com>) will be administered at Baseline (W1), W8 and W20.

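### Exclusion criterion 2 is ambiguous: it ties the 2-month antibiotic exclusion to one course, and nothing in the protocol says how two or more courses are handled

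*Combined protocol and SAP*

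**What the plan says.** Section 3.2 bars anyone who meets a listed criterion. Criterion 2 is "Use of antibiotics within the past 2 months, if the patient received a single course of antibiotic". Directly above it, criterion 1 covers a comparable exposure over the same window with no condition attached: "Use of pre- or probiotics during the past 2 months".

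For Specific Aim 2, section 2.2.1 states that "the primary efficacy end points will be change in microbiome, metabolome and markers of inflammation". Section 3 describes one open-label sequence with "3 sequential phases of (a) 2 weeks of no intervention, (b) 12 weeks of Patiromer treatment, and (c) 6 weeks of no intervention". On stool sampling, section 6.3.4 says "Subjects will be instructed to collect samples from bowel movements at weeks 1, 2, 3, 4, 6, 10, 14, 17, and 20". Medication is dispensed at week 2, so the samples at weeks 1 and 2 are the only ones from before treatment.

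Antibiotics also appear in the sections on monitoring and data collection. Section 6.1.1 says "Detailed information about infection and type of antibiotic used (if any) will be collected", and section 7 has weekly contacts that ask about antibiotic use. At screening, section 6.3.2 says that "medical records from the clinic facility will be reviewed to capture any non-reported data on recent medication use".

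**The concern.** An exclusion meant to keep recent antibiotic exposure out of a microbiome study should become stricter, or at least no looser, as exposure rises. This one, followed word for word, stops at one course.

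What is at stake is the before-and-after comparison. With no concurrent control, each patient's early samples are the reference. If a patient enters shortly after several courses, the gut flora may still be recovering at weeks 1 and 2 and continue to recover through weeks 3 to 14. In that patient, recovery could be taken for an effect of the drug. Section 6.2.2.1, which describes the microbiome analysis, does not mention antibiotic exposure, so nothing stated there would separate the two.

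**Working it through.** The plan gives no figure on this point, so the check is first one of wording and then an illustration of size.

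**1. What each reading does**

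| Courses in the 2 months | Literal reading | Even one course excludes | Tiered rule, second part missing |
|---|---|---|---|
| 0 | not excluded | not excluded | not excluded |
| 1 | excluded | excluded | excluded |
| 2 or more | not barred | excluded | depends on text that is absent |

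Under the second reading the conditional clause adds nothing. Under the third, a rule and its window are missing. A fourth reading, that a single course is permitted, contradicts the conditional word. Criterion 1 shows that the protocol can state an unconditional rule. Criterion 6 shows that it can put two look-back windows in one line (6 months and 3 months). The first contrast makes an any-use rule plausible and the second makes a tiered rule plausible; neither decides the matter.

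**2. Whether another section fills the gap**

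- Sections 4.1, 6.1.1, 6.3.1, 7, 7.1 and 7.1.1 concern monitoring or recording antibiotic use during the study.
- Section 6.3.2 collects recent medication use at screening but sets no limit on courses.
- Criteria 3 and 4 exclude certain infections and bowel conditions. They would catch some heavily treated patients, by diagnosis and not by exposure.

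No section gives a rule for two or more courses.

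**3. Timing under the literal reading**

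A multiple-course patient whose last dose falls just before week 0 gives the two pre-treatment stool samples about 1 and 2 weeks later. This assumes that the 2 months are counted back from screening, which the protocol does not state.

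**4. Possible size (illustration only)**

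Inputs: n = 25 from sections 3 and 3.3. Assumed: k affected patients; each drifts by r = 0.5 to 1 SD on one summary measure after baseline; the SD of within-patient change is 1.

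- Standard error of the mean change = 1/√25 = 0.20 SD.
- Shift in the mean = k × r / 25.

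| k | Shift (SD) | Shift ÷ 0.20 (standard errors) |
|---|---|---|
| 1 | 0.02 to 0.04 | 0.1 to 0.2 |
| 2 | 0.04 to 0.08 | 0.2 to 0.4 |
| 3 | 0.06 to 0.12 | 0.3 to 0.6 |

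A shift of half a standard error is 0.10 SD. It needs 0.10 × 25 / 1 = 2.5, so 3 patients at r = 1, or 0.10 × 25 / 0.5 = 5 patients at r = 0.5. No test or false-positive rate is modelled.

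**The case against.** The strongest reply is that a sensible team will already read the line as excluding any use, so that in practice nobody with several recent courses is admitted. That may be so, but the documents do not say it, and the line still needs an edit under every plausible reading.

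The design also offers some protection, and this part of the reply stands:

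- Two pre-treatment samples may reveal drift before the drug starts.
- Samples at weeks 17 and 20 are taken off drug. A reversible drug effect should fade by then, whereas recovery from antibiotics would not be expected to reverse. A lasting drug effect and continuing recovery would still look alike.
- The screening review of medication and clinic records should bring recent antibiotic use to light, and criteria 3 and 4 remove some of these patients.

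These features reduce the risk without removing it.

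A reader might infer that an any-use rule guarantees a long antibiotic-free interval before baseline. Two months is 59 to 62 days, or 8.4 to 8.9 weeks; adding 1 or 2 weeks gives 9.4 to 10.9 weeks, against 1 to 2 weeks under the literal reading. The documents do not support that contrast. Antibiotics taken between week 0 and week 2 are reviewed and recorded (sections 7 and 7.1) but not barred, and section 3.4.1 does not name them as a ground for withdrawal. Under any reading, a patient could give a baseline sample days after a dose.

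**Conclusion.** Criterion 2 is ambiguous, and its silence on two or more courses is certain from the text. The consequence is much less certain. Its size is unknown, and on the assumed inputs it is probably negligible with one or two affected patients. The number affected, the drift per patient and the SD of change are all assumptions.

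Three stronger conclusions might be drawn, and none is supported:

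- That the authors wrote an inverted rule. This describes only the literal reading; two other readings are plausible and the documents do not choose between them.
- That the microbiome results are compromised. Nothing in the documents shows that a multiple-course patient was enrolled.
- That sites will apply the line differently. Section 3.3 describes a single source: "Subjects will be recruited through a search of the dialysis unit database". The issue is how the screening team reads the line.

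The case for correcting it is that the criterion bears on a named primary efficacy endpoint and costs little to repair, not that a large bias has been shown.

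**What to change.** The investigator should confirm the intended rule and reword criterion 2 so that it states how one course and two or more courses are each handled, and cannot admit the heavier exposure while excluding the lighter. If a second tier was dropped, it should be restored with its own window. The date from which the look-back is counted should be stated as well.

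For anyone already enrolled, use the screening medication history, the record review and the antibiotic reviews at weeks 1 and 2 to flag use from 2 months before entry up to the week 2 sample. Then repeat the microbiome analysis without the flagged patients. This does not deal with antibiotics taken later in the study.

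Cost: one line of protocol text and one sensitivity analysis on data already being collected.

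- **Screening.** If the team already excludes any use and that is the rule confirmed, there is no extra screening. If the rewording removes patients who would have been 1 to 3 of the 25 (an assumption), the planned 120 screened becomes 120/(1 − 1/25) = 125 to 120/(1 − 3/25) = 136.4, so 137. At the planned pace of 120/36 = 3.33 per week, the extra 5 to 17 take 5/3.33 = 1.5 to 17/3.33 = 5.1 weeks.
- **Precision.** Leaving out 1 to 3 patients widens the standard error in the sensitivity analysis by √(25/24) = 1.021 to √(25/22) = 1.066, about 2% to 7%.
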